COVER PAGE

STUDY TITLE: ASSESSMENT OF THREE BASIC PROGRESSIVE LENS DESIGNS

REGISTRATION NUMBER: NCT05252871

DATE: 09/27/2021

STUDY PROTOCOL

STUDY DESIGN:

This study was a non-invasive double-masked randomized clinical investigation. The interventional model was parallel assignment, and the study was triple-masked (participant, investigator, and outcomes assessor). For this study, 83 participants were recruited over a period of 3 months, 80 patients were enrolled into the study, and 3 participants were excluded since they did not meet the inclusion criteria.

STUDY OBJECTIVES:

The primary purpose of the study was to evaluate the preference, adaptability, and visual performance of three basic progressive lens designs.

PRIMARY ENDPOINT:

Evaluation of the preference among progressive lens designs.

STUDY SUBJECTS AND RECRUITMENT:

Study subjects were experienced progressive addition lens wearers, which were recruited by advertisements, by email, and with direct person-to-person solicitation.

Inclusion criteria: 1. Subjects should be experienced progressive lens designs wearers who have worn their current prescription for at least one month; 2. The designated progressive lens designs wearers had no issues about wearing a progressive lens design; 3. Age: 45 to 70 years old; 4. Visual Acuity (decimal): far & near monocular cc ≥ 1.0 ; 5. Normal binocular vision (at distance & near: no strabismus on cover testing, aligning prism of less than 2Δ horizontally or vertically, stereoacuity of 2' or better at distance and near); 6. New prescription (found at visit#1) was in the range: (a) Spherical power: less than $+\/-6.00$ D; (b) Cylindrical power: less than -2.75 D minus cylinder; (d) Addition: 1.50 D - 2.50 D; (e) Difference in the power (spherical equivalent) between eyes: less than 2.00 D; (f) 7. Understanding and speaking English or Spanish to be able to answer questionnaires.

Exclusion criteria: 1. Subjects who have never worn any progressive lens designs or have not worn their current progressive lens design for at least one month. 2. Age: younger than 45 years or older than 70 years. 3. Visual Acuity (decimal): far & near monocular cc < 1.0 . 4. Binocular vision problems (at distance & near: strabismus on cover testing, aligning prism of 2Δ or greater horizontally or vertically, stereoacuity of less than 2' at distance and near). 5. New prescription (found at visit#1) is: (a) Spherical power: more than $+\/-5.75$ D; (b) Cylindrical power: more than -2.50 D minus cylinder; (d) Addition: less than 1.50 D or more than 2.50 D; (e) Difference in the power (spherical equivalent) between eyes: more than 1.75 D; (f) Different from current prescription more than 0.50 D in any meridian 7. Known ocular disease that affect visual acuity. 8. Vertigo or a balance problem.

Potential study subjects were contacted by the study coordinator. At this time, the study coordinator assigned a subject ID and scheduled each subject for their first visit.

PROGRESSIVE ADDITION LENSES:

Each lens pair for each study subject was specifically made to the subject's up-to-date prescription. To assure optimal vision, all lenses possessed anti-reflective coatings and were clear (not tinted). Each frame was fitted to the patient's anatomic features to assure an optimal wearing experience. In addition, all subjects were reminded of the specifics of progressive addition lenses, their appropriate use, and that a short period of visual adaptation might be required.

DATA MONITORING:

Throughout the entire duration of the study, data monitoring was conducted by the Center for Clinical Research at Western University of Health Sciences. This involved checking of consent forms being signed dated, checking for the completion of source documentation and clinical research forms and clinical binders.

STUDY PROCEDURES:

All three visits were conducted in the Eye Care Institute, WesternU Health Pomona, [name].

During Visit #1:

- The visit started with an explanation of the study and a discussion of the informed consent form for which signatures were obtained. Then a set of screening questions was asked.
- Subjects, who meet the inclusion criteria continued in the study, received an eye examination, and a new progressive addition lens prescription.
- Each eligible study subject reported visual experiences with their currently worn progressive addition lenses.
- Each subject then selected one appropriate spectacle frame from a selection of high-quality frames made from titanium material. For this selected frame, the patient's fitting data were obtained.

Between Visit #1 and Visit #2:

- The PI communicated the subject-ID along with the prescription data and the selected spectacle frame model to the spectacle manufacturer. Based on this information, the manufacturer made three pairs of glasses with the different lens designs for each subject. All three pairs were manufactured with the frame model that the patient selected at visit #1. A maximum of one month was planned for production and delivery of the progressive addition lenses.
- The primary investigator, co-investigators and the subject were blinded to which basic progressive lens designs were used by the manufacturer. To reduce evaluation bias stemming from the wearing sequence for the lens design, the PI adopted a stratified permuted block randomization, based on the average lens power data which were computed from the prescriptions found during visit #1. This wearing sequence was assigned for each study subject. During the manufacturing process, the frames had small marks on their temples to distinguish each for the assigned wearing sequence.

During Visit #2:

- Each study subject received three pairs of progressive addition lenses, that were adjusted and fitted. At this time, an assessment of distance and near visual acuity was

conducted. Then the subject evaluated first visual impressions with all pairs, one after another, after 10-15 minutes of wearing time.

- Afterwards, the first pair was handed to the subject and the second and third pairs were placed in sealed envelopes along with one set of evaluation surveys
- Each subject was instructed:
 - to only wear the first assigned (and labelled) pair of progression addition lenses for one week (this is the first week of the trial), while carefully observing the ease of visual adaptation and visual experiences.
 - to only wear the second assigned (and labelled) pair of progression addition lenses in week two of the trial. This pair is also worn for one week, while carefully observing the ease of visual adaptation and visual experiences.
 - to only wear the third assigned (and labelled) pair of progression addition lenses in week three of the trial. This pair is also worn for one week, while carefully observing the ease of visual adaptation and visual experiences.

Between Visit #2 and Visit #3:

- Study subjects wore the three pairs of progressive addition lenses in the sequence explained during visit #2.

During Visit #3:

- During visit #3, each study subject returned with the three pairs of progressive addition lenses. First, an assessment of distance and near visual acuity was conducted. Then, each participant returned all progressive addition lens pairs to the investigator along with the satisfaction questionnaires regarding the adaptability and visual performance for each progressive addition lens pair. Finally, each patient completed a final comparison questionnaire of all 3 progressive addition lens pairs and ranked them as “the best”, “good”, “the worst”. At this point, the study ended for each subject, all 3 pairs of glasses were returned, and subjects were reimbursed for their time and effort.

DATA ANALYSIS:

Data analysis includes Analysis of Variance (ANOVA) or its non-parametric alternatives with post-hoc tests and correlation analysis.

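### Is the masking undone because the principal investigator, listed as masked, also appears to run the wearing-sequence randomisation?

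*Protocol*

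**What the plan says.** The Protocol's Study Design section first states "This study was a non-invasive double-masked randomized clinical investigation", and the next sentence adds that "the study was triple-masked (participant, investigator, and outcomes assessor" were the masked parties.

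Under Study Procedures, in the part covering the interval between the first two visits, four statements bear on allocation:

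- What was concealed, and from whom: "The primary investigator, co-investigators and the subject were blinded to which basic progressive lens designs were used by the manufacturer".
- How the order was randomised: "the PI adopted a stratified permuted block randomization, based on the average lens power data which were computed from the prescriptions found during visit #1".
- How it was applied: "This wearing sequence was assigned for each study subject". No role is named.
- How the pairs were told apart: "During the manufacturing process, the frames had small marks on their temples to distinguish each for the assigned wearing sequence".

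The same part says that "The PI communicated the subject-ID along with the prescription data and the selected spectacle frame model to the spectacle manufacturer" and that "the manufacturer made three pairs of glasses with the different lens designs for each subject".

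The SAP refers to the designs as A, B and C. Neither document names the person who generated the list, the holder of the key from code to design, the block size, the cut-points of the lens-power strata, or the time of unmasking.

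**The concern.** The sentence that masks the PI is followed directly by one that ties the PI, and no other role, to the randomisation. A reader may conclude that the PI produced the order of designs for every subject. On that reading the PI might not know what design A is, but would know which pair was A for each subject. Feedback was available to build on: first impressions of all pairs are collected at the second visit, and pairs and questionnaires come back to the investigator at the third. An opinion formed about one code could then be carried to later subjects.

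The endpoint makes this worth asking. Preference is a ranking by the subject, and the surrounding contact (fitting, advice on adaptation, wearing instructions, the final comparison) takes place at the clinic. If staff expectations reached the subject, the ranking could shift with no record of it. Two different masking labels in consecutive sentences add to the doubt, as does the absence of any named outcomes assessor separate from the investigator and the subject.

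**Working it through.** No power, error-rate or sample-size figure bears on this, so the check is mainly a comparison of the statements.

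**1. What the PI is said to have done.** The verb is that the PI *adopted* a type of randomisation, which describes choosing a method. The sentence on assignment is passive and names nobody. That the PI drew up or kept the list is a possible reading, but it is not stated.

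**2. What the masking covers.** The PI, co-investigators and subject are masked to which design is which. Suppose the PI did generate an order such as B, A, C. The PI's mask to identity would fail only if the list carried true design names, or if the PI also held the key. Neither document says either. The A, B, C labels appear only in the SAP, as analysis labels; nothing places them in front of the PI or staff during the visits.

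**3. What reached the clinic.** The manufacturer made all three pairs in the frame model the subject had chosen. The temple marks were applied during manufacture and distinguish the pairs by place in the wearing sequence. The items listed as going from the PI to the manufacturer are the subject ID, prescription and frame model; the sequence is not among them. The marks depend on the sequence, so either it was sent and not listed, or the manufacturer assigned it. The documents do not settle which.

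**4. Predictability of blocks.** Three pairs can be worn in 3! = 3 × 2 × 1 = 6 orders. The block size is not given. If one assumes a block holding each order once, someone who has seen the first five knows the sixth. In a parallel-group trial that matters because it lets a recruiter choose who enters which arm. Here each subject wears all three designs whatever the order. The randomisation uses prescriptions from the first visit and is described as taking place after that visit, when consent and eligibility are settled. Knowing the next order gives no means of steering a subject towards or away from a design.

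**5. Route to the endpoint.** The subject is stated to be masked and does the ranking. The reminder about adaptation is given to all subjects and is not specific to a design. The second and third pairs go home in sealed envelopes with the surveys, and the three weeks of wear take place away from the clinic.

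**6. Size.** The largest possible exposure is 80 subjects × 3 pairs = 240 wearings. For bias to arise, staff would need to hold a list linking codes across subjects, form an expectation about a code, and convey it to masked subjects strongly enough to alter their rankings. None of these steps is documented.

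**7. The two labels.** Double-masked and triple-masked differ in the count of masked roles. The second sentence names the roles, and the first does not say that any of them was unmasked. Since the subject supplies the primary outcome, subject and outcomes assessor largely coincide for that endpoint, which may explain why both terms were used.

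**The case for a change.** The strongest case is that masking to identity is not enough in a design where everyone wears all three lenses. Someone who holds the sequence list can recognise the same coded design from subject to subject without knowing its name, and can come to favour or distrust it. The subject's own mask does not close that route, because clinic contact surrounds the ranking. Good practice keeps the list away from anyone described as masked. A reader cannot confirm from this text that it was kept away, and a few sentences would settle the matter.

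Part of this stands. The PI's mask cannot be verified from the documents, and a named list-holder, a key-holder and a time of unmasking would have made it verifiable. But the argument needs the PI to have held the list, which the text does not say. It shows that a detail is missing; it does not show that the procedure was wrong. The Protocol is also written in the past tense, with recruitment and enrolment already reported, so moving custody of the list to another party could not alter what was done.

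**Conclusion.** The concern does not hold as a defect in the plan. The labels are inconsistent, which is a clerical slip, and custody of the list and key is not described, which is a gap in reporting. Neither shows that the investigator's or the subject's mask failed. With the PI and the self-ranking subject masked to design, as the Protocol states, the preference comparison is adequately protected.

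The size of any bias cannot be estimated from the documents, and nothing in them indicates that it is above zero. This rests on two assumptions: that any list seen at the clinic did not carry true design names, and that the pairs were identifiable there by wearing order only. The second agrees with the description of the temple marks. The first is not contradicted anywhere. If a list with design names had been in the PI's hands, the PI's mask would have failed and the conclusion would need revisiting. The study report can say who held the list and key as a matter of routine, without any change to design or analysis.

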COVER PAGE

STUDY TITLE: ASSESSMENT OF THREE BASIC PROGRESSIVE LENS DESIGNS

REGISTRATION NUMBER: NCT05252871

DATE: 09/27/2021

DATA ANALYSIS PLAN

DATA ANALYSIS:

Data analysis includes Analysis of Variance (ANOVA) or its non-parametric alternatives with post-hoc tests and correlation analysis:

- Repeated-measures ANOVA or its non-parametric alternatives are conducted since each participant experienced all three lens designs. This allows to assess the main effect of lens design while accounting for the repeated measures within participants. Influencing factors (age group, gender, previous lens design experience, lens power, add power) are included as independent variables to investigate their potential effects on the outcomes.
- Significant differences in the ANOVA or its non-parametric alternatives are further explored through post-hoc tests to determine which specific pairs of progressive lens designs (A, B, or C) or levels of influencing factors (age group, gender, previous lens design experience, lens power, add power) differ from each other.
- Correlation analyses are utilized to investigate the relationships between continuous variables (e.g., age) and the Likert scale responses.

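### Wearing order is randomised because it may bias ratings, but the analysis has no wearing-position term, so any order effect costs power

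*SAP*

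**What the plan says.** The Protocol's Study Procedures give every subject all three lens designs, one per week. The last instruction is "to only wear the third assigned (and labelled) pair of progression addition lenses in week three of the trial". The order is assigned per subject, for a stated reason: "To reduce evaluation bias stemming from the wearing sequence for the lens design, the PI adopted a stratified permuted block randomization". At Visit #3, "Finally, each patient completed a final comparison questionnaire of all 3 progressive addition lens pairs and ranked them as" best, good or worst. The primary endpoint is preference among the designs, so this ranking is its record.

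The SAP's first bullet says "Repeated-measures ANOVA or its non-parametric alternatives are conducted since each participant experienced all three lens designs", and then "Influencing factors (age group, gender, previous lens design experience, lens power, add power) are included as independent variables". Neither document has a term for wearing position, period or sequence. The SAP does not name the non-parametric test or say how the ranking is analysed; for three ranked pairs per subject the usual choice is Friedman's test.

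The Protocol's Study Design section calls the model parallel assignment. That conflicts with its own procedures and with the SAP's repeated-measures analysis.

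**The concern.** The protocol treats wearing order as a source of error and randomises to control it, but the analysis then ignores it. The five added factors are all characteristics of the subject. The factor that varies within a subject along with lens design is the one left out, and Friedman's test has no place for it.

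The documents give reasons why position might matter. Subjects are told that "a short period of visual adaptation might be required". The first pair is worn in the first week of a new prescription and frame, and the third is the most recent when the subject ranks all three.

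Balanced randomisation stops position from favouring one design, but it does not remove the variation that position causes. If that variation is left in the error term, the test is less sensitive than it needs to be on the trial's main question.

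**Working it through.** The documents state no alpha, power, effect size or SD, so there is no planned figure to reproduce.

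**Inputs.** From the Protocol: N = 80 ("80 patients were enrolled into the study", all assumed analysed), three designs, three one-week periods, and order set by stratified permuted blocks. Assumed: two-sided alpha 0.05, position-balanced orders within blocks, the block size and strata, and the sizes of the design and position effects.

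**Bias.** Incomplete blocks leave a small imbalance. Across four simulated layouts (six orders or a three-order Latin square; blocks of 3, 6 or 12; one, three or four strata) the gap in mean wearing position between designs averaged 0.025 to 0.063 positions. At 0.5 SD per week that is 0.5 × 0.025 ≈ 0.01 SD to 0.5 × 0.063 ≈ 0.03 SD, which is negligible.

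**Residual variance, ratings.** Let s be the first-to-third-week shift in within-subject SDs.

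- Linear drift: position effects are −s/2, 0, +s/2, with sum of squares s²/2. Spread over 2(n−1) residual degrees of freedom, this multiplies the residual mean square by 1 + (s²/4) × n/(n−1). The interval-width ratio is about √(1 + s²/4).
- Week 1 only lower by s: the centred sum of squares is 2s²/3, so the ratio is about √(1 + s²/3).

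For s = 1.0: √1.25 = 1.12 (linear) and √1.333 = 1.15 (week 1 only).

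**Power, ratings.** Take a best-to-worst design difference of 0.50 SD, equally spaced. The non-centrality is 80 × 0.50²/2 = 10. The F test has 2 and 158 degrees of freedom and critical value 3.05; without a position term the effective critical value is 3.05 times the inflation factor.

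| Shift s (SD) | Residual inflation | Width ratio | Type I error, no position | Power, no position | Power, with position |
|---|---|---|---|---|---|
| 0 | 1.00 | 1.00 | 5.0% | 81% | 81% |
| 0.5 | 1.06 | 1.03 | 4.2% | 79% | 81% |
| 1.0 | 1.25 | 1.12 | 2.4% | 71% | 81% |
| 1.5 | 1.57 | 1.25 | 1.0% | 59% | 81% |

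Simulation (6,000 runs per setting) agrees within about 2 points: 81, 77, 71 and 57% without position, and 79 to 81% with it. For a smaller design effect (0.36 SD) the simulated figures are 50 vs 50, 46 vs 50, 38 vs 50 and 27 vs 51%. The four layouts give the same picture.

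**Ranking (primary endpoint).** Rankings were simulated from a Plackett-Luce model: N = 80, six orders, blocks of 6, three strata, best-to-worst 0.64 log-odds, 2,500 runs. The same rank-ordered logit was fitted without and with position.

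| First-to-last shift (log-odds) | Last-worn beats first-worn, equal designs | Type I error, no position | Power, no position | Power, with position | Friedman power |
|---|---|---|---|---|---|
| 0 | 50% | 5.0% | 79% | 79% | 78% |
| 0.6 | 65% | 4.6% | 74% | 76% | 73% |
| 1.2 | 77% | 2.7% | 61% | 73% | 61% |
| 1.8 | 86% | 1.2% | 41% | 67% | 42% |

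Type I error with position was 5.2 to 5.6%. A separate set of 1,500 runs gave power within 2 points. Friedman tracks the unadjusted logit, so the gap comes from the position term and not from the change of test. With normal utilities instead (best-to-worst 0.52 SD; shifts 0, 0.5, 1.0, 1.5 SD) power was 68 vs 69, 67 vs 69, 54 vs 65 and 40 vs 62%.

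**The case against.** The best counter-argument is about size. The large losses need wearing order to matter two to three times as much as the lenses. When the two effects are about equal, the loss is 2 to 4 points; for the ratings, a loss of 5 points needs a shift of about 0.75 SD. The documents lean towards a small effect: subjects are experienced wearers without problems, a prescription change above 0.50 D is an exclusion, all three pairs share one prescription and frame model, and at Visit #2 each subject tries all three for 10 to 15 minutes before week 1. Randomised order already deals with bias, and a conservative test remains valid.

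All of that is fair and limits how strongly the point can be put. It does not rule out a position effect, particularly recency at the final ranking, and it gives no reason to leave the term out.

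Three further objections stand as qualifications:

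- The SAP does not name Friedman or say how the ranking is tested, so the ranking comparison rests on an inferred method.
- The main ranking simulation uses the model that the rank-ordered logit assumes, and that test's type I error is slightly above 5%, so a gap such as 74 vs 76% should not be pressed. The normal-utility check shows that the larger gaps do not depend on that model.
- The documents record the assigned order, not the order actually worn at home. Assigned order is sufficient for the analysis.

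**Conclusion.** The concern holds. The listed analysis omits a within-subject factor that the protocol itself identifies, and any position effect will be counted as error. The consequence is lost precision and power, not bias or false positives. For a first-to-third-week shift of 0.5, 1.0 or 1.5 SD, ratings intervals are 3, 12 or 25% too wide and power falls by about 2, 9 or 22 points from 81%. Power for the ranking falls short of the position-adjusted analysis by 2, 12 and 26 points at the three non-zero shifts examined.

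These sizes depend on an assumed position effect, for which the documents give no figure and which may be small or zero. The conservative direction assumes blocks built from position-balanced orders, which the protocol does not list. Under simple randomisation, type I error would be about nominal but power would still be lost. Carryover between weeks was not modelled. The plan should be changed because the correction is cheap; the omission is not a fatal flaw.

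**What to change.** Add to the SAP: *Wearing position (1, 2, 3) is a within-subject fixed factor in every repeated-measures model that compares lens designs. The Visit #3 ranking is analysed with a rank-ordered logit containing lens design and the assigned wearing position of each pair; design is tested by a likelihood-ratio test on 2 degrees of freedom.* Friedman's test can stay as a supportive analysis. A term for the previously worn design is optional, as a sensitivity analysis only. State the set of orders, the block size and the strata. In the Protocol, replace the parallel-assignment label with a randomised three-period crossover; this is a wording correction.

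The ratings model loses 2 of about 158 residual degrees of freedom. The ranking needs a somewhat more complex method, available in standard software, and at large shifts it restores only part of the lost power. No new data are required, since the sequence was assigned per subject and the frames were marked for it. The change should be dated and, if still possible, made before the lens designs are unmasked; otherwise it should be reported as post hoc.
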